5. STUDY POPULATION

5.1 General Considerations

The Investigator is expected to invite all subjects expected to meet the study entry criteria to participate in the study.

5.2 Inclusion Criteria

Pre-operative:

1. Adult subjects \geq 18 years requiring elective/non-emergent open or laparoscopic general, gynaecological, cardiothoracic, or urological surgical procedures;
2. Subject or authorised representative has signed the approved Informed Consent;
3. Subject(s) whose International Normalised Ratio is <1.5 within 24 hours of surgery.

Intra-operative:

4. Presence of an appropriate Target Bleeding Site (TBS) identified intra-operatively by the surgeon;
5. Subject(s) undergoing cardiothoracic surgery with anticoagulation must have anticoagulation reversed prior to TBS identification and treatment.

5.3 Exclusion Criteria

Pre-operative:

1. Female subjects who are pregnant or nursing;
2. Subject on anticoagulant medication (with the exception of aspirin) prior to surgery. Washout periods for respective medications must be observed. If information is not readily available within the Instructions for Use (IFU), a conservative approach should be taken and intravenous heparin stopped 12 hours prior to surgery and 2 days prior for oral medication;
3. Subject on antiplatelet/P2Y12 inhibitor medication prior to surgery. Platelet recovery times for respective medication must be observed. If information is not readily available within the IFU, a conservative approach should be taken and medication stopped 5 days prior to surgery
4. Subject is currently participating or plans to participate in any other investigational device or drug without prior approval from the Sponsor;
5. Subjects who are known, current alcohol and/or drug abusers;
6. Subjects with any pre-operative findings identified by the surgeon that may preclude conduct of the study procedure.

Intra-operative:

7. Subjects with any intra-operative findings identified by the surgeon that may preclude the use of study product;
8. Subject with TBS in an actively infected field [Class III Contaminated or Class IV Dirty or Infected (see Section 15.2, Appendix 2);
9. TBS is on arteries or veins where application of SURGICEL Powder would present a risk of introducing the study product into an open blood vessel;
10. Major arterial or venous bleeding or major defects in arteries and veins;
11. TBS where silver nitrate or any other escharotic chemicals have been applied;
12. TBS is in, around, or in proximity to foramina in bone, or areas of bony confine, the spinal cord, or optic nerve and chiasm;
13. TBS in urological procedures where plugging (blocking) of the urethra, ureter or a catheter is possible by the study product.

6. INVESTIGATIONAL PRODUCT

6.1 SURGICEL Powder “Open-Tip” Applicator and Endoscopic Applicator

SURGICEL Powder is an absorbable haemostatic powder made of oxidised regenerated cellulose (ORC), which is prefilled in a sterile, single-use, “open-tip” applicator that dispenses the powder on a target intraoperative bleeding site during open procedures (Figure 1).

The applicator is provided sterile with 3 grams of SURGICEL Powder. The “open” tip applicator enables surgeons to topically apply powder to a desired anatomical site by manually compressing the bellows. The tip is flexible such that the surgeon can angle the tip in the direction of bleeding. The applicator is provided in the “closed” or “off” position so powder cannot be expressed.

The ORC powder is developed by producing fibrillar structured aggregates of ORC fine fibres using a proprietary process. The powder has a unique physical morphology; however, it maintains the chemical and bactericidal properties of the original ORC fabric. The ORC aggregates in SURGICEL Powder penetrate the surface layer of blood, initiating clotting and adhering to tissue for durable and sustained haemostasis. Because the ORC aggregates are chemically identical to ORC fabric products, they share key attributes and perform in ways that will be familiar to surgeons. Both induce haemostasis rapidly; both turn a dark reddish-black on exposure to blood; both are absorbed within approximately 2 weeks; and, both are bactericidal in vitro for a wide range of organisms^{iv}.

[figure not shown]
SURGICEL Powder (“Open Tip” Attached)

Figure 1: SURGICEL Powder Device

The image provided above is for illustration purposes only and may not represent the actual device.

The SURGICEL Endoscopic Applicator is a Class IIa accessory device that will be packaged and sold separately for use with the SURGICEL Powder device in endoscopic/laparoscopic procedures. As shown in Figure 2, the open tip is removable and can be replaced with the SURGICEL Endoscopic Applicator (also referred to as “lap tip”).

The SURGICEL Endoscopic Applicator is supplied with a flexible inner tip and a rigid cannula and is designed to mate with the SURGICEL Powder Device, allowing for the delivery of SURGICEL Powder to a bleeding surgical site through a 5-mm or larger trocar (Figure 2).

SURGICEL Powder Endoscopic Applicator

Removal of Open Tip Applicator

Figure 2: SURGICEL Endoscopic Applicator - Interchangeable with Open Tip

The images provided above are for illustration purposes only and may not represent the actual device.

6.1.1 Labelling and Packaging

SURGICEL Powder is packaged on an inner card which is further packaged inside an outer pouch composed of polyester laminated foil with an inner heat seal coating serving as a barrier to moisture and contamination.

The foil pouches are packed into a cardboard box as secondary packaging.

Labelling may include the following:

- Do not reuse
- Do not resterilise
- Do not use if package is damaged
- Caution
- Use-by date
- Temperature limit
- Manufacturer Catalogue number
- Batch code
- Sterilised using Irradiation
- CE Mark and Identification Number of Notified Body. The product meets the essential requirements of Medical Device Directive 93/42/EEC
- Authorised Representative in the European Community
- Quantity

6.1.2 Shipping, Handling and Storage Conditions

Shipping conditions should be 15° to 30 °C.

Store unopened packages of SURGICEL Powder at controlled room temperature 15° to 30 °C. SURGICEL Powder does not require refrigeration. Do not freeze. Do not use if package is opened or damaged. Sterility is guaranteed unless package is opened or damaged.

The applicator is provided sterile with 3 grams of SURGICEL Powder (ORC) and should not be re-sterilised/reused. Do not re-sterilise/reuse SURGICEL Powder or the SURGICEL endoscopic tip. Once opened, keep dry prior to use, so that it can remain in the sterile field throughout the surgery. Disposal of the device, the endoscopic tip (if used for appropriate surgery) and packaging will be in accordance with study facility policies and procedures regarding biohazardous materials and waste.

Distribution of SURGICEL Powder and the endoscopic accessory to the clinical sites will be performed by ETHICON Clinical Operations.

6.1.3 Preparation

SURGICEL Powder device with “open tip” applicator is prefilled with 3 grams of powder. The SURGICEL Powder “open tip” and the endoscopic tip are supplied sterile and ready to use out of the package. Only undamaged packages should be used. Once the foil pouch is opened, re-sterilisation is not possible. The following procedure for opening and applying the product should be followed to ensure that the sterility of SURGICEL Powder is maintained.

Non-sterile nurse / Study Personnel

Open outer foil pouch and transfer SURGICEL Powder delivery device and inner card to sterile field. If an endoscopic procedure, repeat the above for the endoscopic accessory.

Sterile nurse / field

Hold the body of the applicator, remove SURGICEL Powder delivery device from inner card and twist to open.

SURGICEL Powder delivery device is now ready for use. If an endoscopic procedure, repeat the above and replace the “open tip” attachment with the endoscopic accessory as per the IFU.

6.1.4 Dose, Route and Duration of Administration

For each subject, 2 applicators of SURGICEL Powder will be available in the theatre and ready for administration prior to TBS identification. Apply an adequate amount of SURGICEL Powder to cover the entire TBS. Use of a non-adhering substrate to apply pressure may prevent adhesion of the formed clot to the surgical glove or other instrumentation.

See application procedures in Section 7.1.3. Additional information can also be found in the IFU.

6.2 Investigational Product Dispensation and Accountability

The Principal Investigator or responsible person designated by the Principal Investigator must account for all study devices throughout and, at the end of, the clinical study. A dispensing log will be kept by the designated study personnel. This log will contain information on the date of administration, subject ID#, lot number, quantity of SURGICEL Powder dispensed, details of any remaining product, subsequent destruction (if applicable). The Principal Investigator must allow the study monitor access to the secured facility where the study devices and/or products are stored during the clinical trial to check inventory and verify the dispensing log. The study product will be stored according to the IFU and be kept in a secured area with access restricted. Study product is to be used for study subjects only.

6.2.1 Topical Haemostats

The use of any other topical haemostats will be permitted on non-target bleeding sites and must be used according to their respective labelling and the Investigator’s usual practice. Haemostatic assessment of any additional bleeding sites treated with SURGICEL Powder will **not** be recorded. Details of all topical haemostats used for the subject throughout the procedure will be recorded on the Concomitant Medication CRF.

6.2.2 Documentation of Concomitant Medications

Indication and start-stop dates of concomitant medications administered from 24 hours prior to surgery up to the 30-day follow up will be recorded. This will include medications used chronically (even if temporarily halted for surgery) and those medications administered as a prophylactic before, during and after surgery.

Anaesthetics used for study surgery and over the counter (OTC) drugs will not be recorded as concomitant medication (except for aspirin, which should be documented). Concomitant

medications used to treat Adverse Events (even if the concomitant medication is an OTC drug or nutritional supplement) must also be documented.

7 STUDY EVALUATIONS

7.1 Study Procedures

The schedule of assessments included in the protocol summary, summarises the frequency and timing of the study procedures. All assessments will be performed by the Investigator or other study personnel with delegation of authority. Data collected for the subject during the study will be recorded in the subject's medical records and study worksheets/source documents, as appropriate, and recorded into the eCRF.

7.1.1 Screening

Prospective subjects will be screened within 21 days prior to surgery. The following activities and tests will be performed at the screening visit. The timing of these activities may occur based on routine hospital practice but may be done up to the day of, but prior to, the surgical procedure.

- Informed consent
- Allocation of screening number
- Documentation of demography (age, gender, race/ethnic origin)
- Physical examination as per normal procedure
- Documentation of relevant medical and surgical history
- Review of Inclusion / Exclusion criteria to confirm subject pre-operative eligibility (section 5.2 and 5.3). If a subject is not eligible, the reason will be documented on the worksheet/screening log

7.1.2 Baseline Assessments

The following activities will be performed within 24 hours prior to the procedure. The timing of these activities may occur based on routine hospital practice and may overlap with some of the screening visit activities (see section 7.1.1).

- Review of inclusion / exclusion criteria to confirm subject pre-operative eligibility (section 5.2 and 5.3). If a subject is no longer eligible, the reason for the screen failure will be documented on the source documentation and screening log
- Documentation of all concomitant medications as stated in Section 6.2.2
- Documentation of any changes in medical history since the screening visit (if done at a separate visit from Baseline)
- Serum or urine pregnancy test (if applicable)
- Coagulation blood tests (PT, aPTT, INR)
- International Normalised Ratio is <1.5 within 24 hours of surgery

7.1.3 Surgical Procedure

The surgeon will use his/her standard surgical techniques for the surgical procedure.

The TBS will be defined as the first active bleeding site identified during dissection, related to the primary operative procedure requiring an adjunctive haemostat. The TBS will be the only site assessed for haemostatic effectiveness.

Once the TBS is identified and conventional techniques were considered impractical or ineffective the surgeon will apply SURGICEL Powder at the TBS to cover the entire bleeding area. The bleeding severity will describe the intensity of the bleeding that is present at the time the surgeon determines that an adjunctive haemostatic product is required.

As a frame of reference, the following scale of bleeding intensity will be utilised. Only target bleeding sites with mild or moderate bleeding as defined by this scale will be included:

Mild Bleeding: A TBS with a small area of capillary, arteriole or venule oozing.

Moderate Bleeding:

1. A TBS with a **larger area** of capillary, arteriole, or venule oozing that presents a significant challenge because of the larger area involved, increasing the volume of blood loss.
- Or*
2. A TBS with bleeding that is more pronounced than oozing, that could also come from a small artery or vein, but is not massive, pulsatile, and flowing.

Severe Bleeding (excluded by this protocol):

Bleeding (arterial, venous, or mixed) that is rapidly flowing, pulsatile or spurting that in the surgeon's judgment requires rapid control to prevent hemodynamic consequences (e.g. hypovolemia, tachycardia, or hypotension) and could involve major volume loss which if not treated rapidly could be life threatening. SURGICEL Powder should not be used in place of sutures or other forms of mechanical ligation for the treatment of major arterial bleeding.

Refer to the IFU for detailed instructions on the application of SURGICEL Powder.

Types of Surgical Procedures

Open, laparoscopic or thoracoscopic surgical procedures may include the following surgical specialties:

- General
- Gynaecological
- Cardiothoracic
- Urological

Examples of types of surgical procedures considered for this study may include (but are not limited to):

- Colectomy
- Low anterior resections
- Retroperitoneal tumour resection

- Liver resection
- Soft tissue bleeding after adhesiolysis
- Hernia repair
- Radical hysterectomy
- Lymphadenectomy
- Tumour removal surgery
- Simple or radical nephrectomy
- Kidney tumour resection
- Adrenalectomy
- Radical cystectomy
- Radical prostatectomy
- Pyeloplasty
- Diffuse bleeding on visceral or parietal pleura
- Soft tissue in cardiothoracic procedures.

The following activities will be performed and information will be collected during the surgical procedure:

- Review of inclusion and exclusion criteria to confirm intra-operative eligibility. If a subject is no longer eligible, the reason for the screen failure will be documented in the source documentation and the screening log
- Medications as outlined in Section 6.2.2
Hospital admission date (for overall Length of Stay)
- Theatre details:
 - Entry and exit time
 - Procedure time (first incision to final wound closure)
 - Transfusion information (if applicable)
- Primary Operative Procedure information: *Open, Laparoscopic, Thoracoscopic. Surgical specialty (General, Cardiothoracic, Gynaecological, Urological) and the type of procedure)*
- Haemostatic methods used at the TBS prior to SURGICEL Powder application [*none, (other methods are impractical), suture, ligation, cautery, other*]
- TBS information: *Parenchyma or soft tissue type and location*
- Type of bleeding (*mild or moderate*)
- Size of TBS (*length, width*)
- Heparin use and time of reversal (if applicable)
- Total number of applicators (units) used
- Adverse events, including any complications that may be related to bleeding and/or thrombotic events.
- Surgeon Ease of Use Questionnaire– one questionnaire needs to be completed per Investigator for their first 2 cases using SURGICEL Powder for open procedures. One questionnaire needs to be completed per Investigator for their first 2 cases using the Endoscopic Applicator (completed as soon as possible, but within approximately 72 hours).

Pre-Treatment Procedures :

- SURGICEL Powder will be available in the theatre, ready for administration to each subject.
- When the surgeon encounters the first appropriate TBS with mild or moderate bleeding in the parenchyma or soft tissue related to the primary operative procedure where conventional methods of control (i.e. suture, ligature, cautery) are ineffective or impractical, the subject can be considered for treatment with SURGICEL Powder.

Treatment Application

Upon completion of application of SURGICEL Powder to the TBS, the stopwatch will be immediately started, (T₀) and the time on the wall clock will be recorded.

Haemostasis will be assessed at 3 minutes, 5 minutes and 10 minutes post SURGICEL Powder application and at initiation of final fascial closure for all subjects.

SURGICEL Powder should be applied dry so should **not** be moistened with water or saline prior to application. Apply an adequate amount of SURGICEL Powder by compressing the bellows, to cover the entire TBS. Depending on the bleeding intensity and anatomical location, more than one layer may be needed to achieve complete haemostasis. After SURGICEL Powder application to the TBS, the surgeon may apply pressure over the treatment site, as needed. Use of non-adhering substrate to apply pressure may prevent adhesion of the formed clot to the surgical glove or surgical instrumentation.

SURGICEL Powder is absorbable and may be left in situ, it is advisable to remove excess powder with irrigation and aspiration once haemostasis is achieved, without disturbing the clot.

In the event of continued bleeding or re-bleeding at the TBS at any time prior to initiation of final fascial closure, the surgeon may add additional SURGICEL Powder, if clinically appropriate, or revert to their institutional standard of care.

If the surgeon feels re-bleeding is due to insufficient coverage of the bleeding area, additional SURGICEL Powder may be applied.

HAEMOSTASIS ASSESSMENT (TIME TABLE):

T₀	Start time. When SURGICEL Powder application is complete (entire TBS covered)
T₃	TBS Bleeding assessment 3 minutes following T ₀
T₅	TBS Bleeding assessment 5 minutes following T ₀
T₁₀	TBS Bleeding assessment 10 minutes following T ₀
T_F	TBS bleeding assessment post the 10-minute assessment, immediately prior to the initiation of final fascial closure

Time to Haemostasis Assessment:

- The Investigator is required to call out once he/she has completed application of the product (defined as adequate coverage including additional layer, if needed) - at the same time, the **stopwatch must be started and the wall clock recorded** by study personnel (**T₀**).
- The TBS will be assessed at the time points 3 minutes (**T₃**), 5 minutes (**T₅**), and 10 minutes (**T₁₀**) following application for assessment of haemostasis.
- The Investigator must evaluate for haemostasis at the TBS immediately prior to the initiation of final fascial closure (last time TBS is visible to confirm haemostasis, **T_F**).
- Haemostasis will be defined as no detectable bleeding from the TBS.
- In the event of continued bleeding or re-bleeding at the TBS at any time prior to closure, the surgeon may add additional SURGICEL Powder, if clinically appropriate, or revert to their institutional standard of care. Information on the treatment methods of re-bleeding/continuous bleeding at the TBS must be recorded.

Success/Failure Assessment for the Binary Primary and Secondary Effectiveness Endpoints

- During the 10-minute assessment period and following the initial application of SURGICEL Powder, the surgeon may reapply SURGICEL Powder. The subject will be considered a failure for preceding binary primary and secondary effectiveness endpoints [e.g. if subjects achieve haemostasis at 3 minutes and re-bleeding occurs at 6 minutes, then the subject will be considered a failure for the preceding effectiveness endpoints (at 3 and 5 minutes)].
- Reapplication of SURGICEL Powder does not have an impact on the success/failure evaluation of subsequent binary effectiveness endpoints (e.g. if haemostasis is achieved by reapplication of SURGICEL Powder, the subsequent binary endpoints will not be impacted. If any additional SURGICEL Powder is applied to the TBS and the TBS is haemostatic at the 10-minute assessment period and maintained up until initiation of final fascial closure, the subject will be considered a success for the effectiveness 10-minute endpoint).
- If during the 10-minute assessment period the TBS requires further haemostatic measures (other than additional application of SURGICEL Powder), the surgeon should perform these measures, and the subject will be considered a failure for all binary primary and secondary effectiveness endpoints (at 3, 5, and 10 minutes).
- Any intra-operative bleeding or any haemostatic measures at the TBS after 10 minutes and prior to initiation of final fascial closure will be considered a failure for all binary primary and secondary effectiveness endpoints.

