8.3 Effectiveness

8.3.1 Effectiveness Variables

The following primary endpoint will be analysed using the ITT and per protocol sets:

- Proportion of subjects achieving haemostatic success at **5** minutes following the application of SURGICEL Powder with no re-bleeding requiring additional treatment at the TBS any time prior to initiation of final fascial closure.

The following secondary endpoints will be analysed using the ITT set only:

- Proportion of subjects achieving haemostatic success at **3** minutes following the application of SURGICEL Powder with no re-bleeding requiring additional treatment at the TBS any time prior to initiation of final fascial closure.
- Proportion of subjects achieving haemostatic success at **10** minutes following the application of SURGICEL Powder with no re-bleeding requiring additional treatment at the TBS any time prior to initiation of final fascial closure.

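### Bleeding at the target site after 10 minutes that needs no treatment is a success by the endpoint sentence and a failure by the 7.1.3 scoring rules

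*Protocol*

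**What the plan says.** Sections 1, 3 and 8.3.1 define the primary endpoint as the proportion with haemostatic success at 5 minutes "with no re-bleeding requiring additional treatment at the TBS any time prior to initiation of final fascial closure". The secondary endpoints at 3 and 10 minutes carry the same condition. None of these sections defines haemostatic success further.

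Section 7.1.3 contains a set of scoring rules headed "Success/Failure Assessment for the Binary Primary and Secondary Effectiveness Endpoints". Its last bullet covers the period after the 10-minute assessment: "Any intra-operative bleeding or any haemostatic measures at the TBS after 10 minutes and prior to initiation of final fascial closure" makes the subject a failure for all binary primary and secondary endpoints.

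Section 7.1.3 also defines the observation on which both texts depend: "Haemostasis will be defined as no detectable bleeding from the TBS". It requires a late look in every subject (T_F): "The Investigator must evaluate for haemostasis at the TBS immediately prior to the initiation of final fascial closure". If the site bleeds again, the surgeon may treat it but is not obliged to.

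Section 8 opens by saying that the SAP will be based on, and will supplement, the statistical section. Section 8 repeats the endpoint sentence and does not cite the 7.1.3 rules.

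**The concern.** The two texts use different triggers. In the endpoint sentence, late re-bleeding matters only if it requires additional treatment. In the last 7.1.3 bullet, bleeding and haemostatic measures are joined by *or*, so bleeding alone is enough.

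The numerator of the primary proportion is at stake. The 5-minute rate and its Clopper-Pearson interval are the main effectiveness result of an open-label, single-arm study in which the investigator makes the assessment. A programmer working from section 8.3.1 and a site scoring by 7.1.3 could classify the same subject differently, at all three time points together.

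**Working it through.** **Can the case arise?** Haemostasis means no detectable bleeding, T_F is checked in all subjects after the 10-minute assessment, and treatment of re-bleeding is at the surgeon's discretion. Mild bleeding, as the protocol defines it, includes oozing from a small area. A minor ooze seen at or before T_F and judged to need nothing is therefore possible under the protocol's own procedures.

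**Side-by-side scoring** of a subject who is dry at 3, 5 and 10 minutes:

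| Event after 10 minutes, before fascial closure starts | Endpoint sentence (1, 3, 8.3.1) | Last bullet of 7.1.3 |
|---|---|---|
| No bleeding, no measure | Success | Success |
| Bleeding that requires treatment, given or not | Failure | Failure |
| Bleeding that does not require treatment | Success | Failure at 3, 5 and 10 minutes |

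Only the third row conflicts.

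**The plan's own figure (section 8.1).** Inputs: n = 100 evaluable subjects, 85 successes, two-sided 95% Clopper-Pearson interval.

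- Lower limit = 0.025 quantile of Beta(x, n − x + 1) = Beta(85, 16): 76.47%.
- Upper limit = 0.975 quantile of Beta(x + 1, n − x) = Beta(86, 15): 91.35%.
- Half-width = (91.35 − 76.47)/2 = 7.44 points, which agrees with the stated 7.4%.

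**Effect of the discrepancy.** Let k be the number of subjects per 100 in the third row. The protocol gives no frequency, so k is an assumption. If the endpoint sentence gives 85/100, the 7.1.3 rule gives (85 − k)/100:

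| k | Rate by 7.1.3 | 95% CI |
|---|---|---|
| 0 | 85% | 76.5 to 91.4 |
| 1 | 84% | 75.3 to 90.6 |
| 2 | 83% | 74.2 to 89.8 |
| 3 | 82% | 73.1 to 89.0 |
| 5 | 80% | 70.8 to 87.3 |

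The shift is 1/n per subject, or 1.0 point at n = 100. The primary analysis uses the ITT set, which contains the evaluable set. If the target of 100 evaluable subjects is met, 1.0 point is therefore the most that one subject can move the primary rate. In this case 7.1.3 is the stricter text, so the rate can only fall or stay the same.

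**The case against.** The strongest reply is that there is nothing to choose between: a short endpoint sentence with detailed scoring rules elsewhere is a normal structure. The heading "Success/Failure Assessment for the Binary Primary and Secondary Effectiveness Endpoints" shows what the 7.1.3 rules are for, and section 8.3.2 uses nearly the same term for these endpoints. Much of this stands, and 7.1.3 is very probably the intended scoring. But the protocol never says that it governs. If it does govern, the treatment condition in the sentence is wrong for the period after 10 minutes, and that condition stands in the section on which the SAP is to be built.

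A reader might infer more than the text supports:

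- **That any untreated late bleeding is in conflict.** It is not. The sentence turns on bleeding that requires treatment, so bleeding that needed treatment and received none fails under both texts.
- **That the texts also conflict over events before 5 minutes.** Powder re-applied at 4 minutes could look like a failure by the sentence, although 7.1.3 says "Reapplication of SURGICEL Powder does not have an impact on the success/failure evaluation of subsequent binary effectiveness endpoints". A suture at 4 minutes could look like a success by the sentence, although 7.1.3 makes it a failure. These two inferences need opposite readings of the same sentence, and a natural reading is available in each case that agrees with 7.1.3. Neither is a contradiction in the text, and without them there is no basis for saying that the rate could move in either direction.
- **That the timing of reapplication is not collected.** Section 7.1.3 says "Information on the treatment methods of re-bleeding/continuous bleeding at the TBS must be recorded" and does not mention timing. However, its list of items collected during surgery is not complete: it omits even the haemostasis results at each time point. The eCRF was not available, so silence does not show that the item is missing.

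**Conclusion.** The contradiction is real and narrow. It concerns subjects who are haemostatic at 3, 5 and 10 minutes and then have TBS bleeding, before fascial closure starts, that does not require treatment. They are successes by sections 1, 3 and 8.3.1 and failures at all three time points by 7.1.3.

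Each such subject costs 1 point at n = 100. How many there will be cannot be determined from the protocol, and there may be none. The worked intervals assume 85 successes in 100 under the endpoint sentence, which is the protocol's own planning rate.

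The analysis is descriptive, with no hypothesis test or success threshold, so no error rate is affected. The 7.4% half-width is correct and does not depend on this point. The change is still worth making, because one rule should fix the numerator of the primary result before anyone scores it.

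**What to change.** In sections 1, 3 and 8.3.1, state that success or failure at 3, 5 and 10 minutes is scored by the Success/Failure rules of section 7.1.3 as written. Align the treatment condition in the endpoint sentence with the post-10-minute rule so that the two no longer disagree. Do this before data are scored. No new definition is needed.

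The cost is a wording amendment in three sections. The design, sample size and precision statement stay as they are. The one drawback is that the reported rate may be slightly lower than under the endpoint sentence alone.
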